- Any clinically significant abnormality identified at the time of run-in (Week -7) or screening (Week -3) that in the judgment of the Investigator or any sub-Investigator would preclude safe completion of the study or constrain endpoints assessment such as major systemic diseases, patients with short life expectancy.
- Considered by the Investigator or any sub-Investigator as inappropriate for this study for any reason, e.g.:
 - Deemed unable to meet specific protocol requirements, such as scheduled visits.
 - Deemed unable to administer or tolerate long-term injections as per the patient or the investigator.
 - Investigator or any sub-investigator, pharmacist, study coordinator, other study staff or relative thereof directly involved in the conduct of the protocol, etc.
 - Presence of any other conditions (e.g., geographic, social) actual or anticipated, that the investigator feels would restrict or limit the patient's participation for the duration of the study.

E 29. Laboratory findings during the screening period (not including randomization Week 0 labs):

- Positive test for Hepatitis B surface antigen
- Positive test for Hepatitis C antibody (if positive, then confirmed by Hepatitis C Virus [HCV] polymerase chain reaction [PCR]).
- Positive serum beta-human chorionic gonadotropin (hCG) or urine pregnancy test (including Week 0) in women of childbearing potential
- Fasting TG >400 mg/dL (>4.52 mmol/L) (1 repeat lab is allowed)
- Estimated glomerular filtration rate (eGFR) <30 mL/min/1.73 m² according to 4-variable Modification of diet in renal disease (MDRD) Study equation (Calculated by central lab)
- ALT or AST >3 x upper limit of normal range (ULN) (1 repeat lab is allowed)
- CPK >3 x ULN (1 repeat lab is allowed)
- Thyroid stimulating hormone (TSH) <lower limit of normal range (LLN) or >ULN (1 repeat lab is allowed. For patients with thyroid replacement therapy, refer to E 17.).

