2.4.5.3 Analyses of laboratory variables

The summary statistics (including number, mean, median, Q1, Q3, SD, minimum and maximum) of all laboratory variables (central laboratory values and changes from baseline) will be calculated for each visit or study assessment (baseline, each post-baseline value of the treatment period, last on-treatment and worst on-treatment value) by treatment group. In addition, for some parameters of interest, mean changes from baseline with the corresponding SE could be plotted over time (at same time points) in each treatment group. This section will be organized by biological function as specified in [Section 2.1.4.3](#). For glucose, only fasting samples will be summarized.

The incidence of PCSAs (list provided in [Appendix A](#)), as well as ALT increase as defined as AESI and hemoglobin decrease from baseline $\geq 15\text{g/L}$ (see [Section 2.1.4.1](#)), at any time during the TEAE period will be summarized by biological function and treatment group irrespective of the baseline level and/or baseline level and/or according to the following baseline status categories:

- Normal/missing
- Abnormal according to PCSA criterion or criteria

Glucose (quantitative summary and PCSA) will also be analyzed, overall and according to the diabetes status at baseline defined in [Section 2.1.1](#).

CPK (PCSA) will also be analyzed, overall and according to prior history of side effects caused by statin.

For parameters for which no PCSA criteria are defined, similar table(s) using the normal range will be provided.

Hepatitis C

Analysis of hepatitis C will be done for patients below according to analysis period.

- DBTP (Hepatitis C planned to be tested for patients who prematurely discontinue study treatment during DBTP) in safety population.
- Alirocumab exposed period (at first step analysis only) (Hepatitis C planned to be tested for patients who prematurely discontinue study treatment during alirocumab exposed period) in alirocumab safety population.
- OLTP: in OLT population.

The number and percentage of patients with a post-baseline seroconversion for hepatitis C test will be provided by treatment group in post-baseline (including the TEAE and post TEAE periods) as well as in the TEAE period alone. Post-baseline seroconversion is defined for patients with a negative baseline status who had either a “positive ribonucleic acid” (RNA) or a “confirmed

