positive antibody (Ab) with negative RNA” post-baseline status as defined in the table below. Other situations require case by case evaluation and will be described individually if relevant.

The status as regards to hepatitis C virus (HCV) for a patient will be defined as follows for all evaluations (baseline and post-baseline).

Table 1 - Definition of the patient status regarding hepatitis C virus

| Antibody test result | Hepatitis C | | | | |
|--|---------------------------------------|------------------|-----------------------------------|------------------|--------------------------------|
| | Negative | | Positive | | |
| Reflexive test ^a – hepatitis C RNA test | Not available or HCV RNA not detected | HCV RNA detected | HCV RNA not detected ^b | HCV RNA detected | Not available |
| Hepatitis C status - label | Negative | Positive RNA | Negative ^b | Positive RNA | Positive Ab – no RNA available |

^a Test performed at the same time or after the antibody test in the pre-treatment period (for baseline evaluation), or post-baseline, respectively

^b For post-baseline evaluation, a second antibody test with a different type of assay is to be done at the same date or after the first antibody test. The result of this test will modify the final hepatitis C status of the patient in some cases (see details in the text below the table)

The baseline evaluation will be based on tests performed during the pre-treatment period.

In case of multiple hepatitis C tests available for the post-baseline evaluation, the positive status of the patient will be defined as follows:

- “Positive RNA” status if at least one post-baseline positive RNA is detected, regardless of status of the patient at the end of treatment.
- Else “Positive Ab – no RNA available” status if no post-baseline reflexive RNA test is available for at least one post-baseline positive antibody test.

If no antibody test is available or with “indeterminate” as result pre-treatment or post-baseline, respectively, the RNA test (if available) will be used alone to determine the status of the patient. If no RNA is available then the hepatitis C status of the patient will be missing.

The post-baseline status “confirmed positive antibody with negative RNA” will replace “Negative” status as defined above in the case where no RNA was detected post-baseline and the 2 antibody tests surrounding the same visit (from 2 different types of assay) are positive.

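### The hepatitis C seroconversion rule counts an unchanged antibody-positive, RNA-negative patient as a conversion when the second antibody assay, specified only after baseline, is also positive

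*SAP*

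**What the plan says.** The rule has four parts, all in the hepatitis C part of SAP 2.4.5.3.

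- **One status table for both times.** "The status as regards to hepatitis C virus (HCV) for a patient will be defined as follows for all evaluations (baseline and post-baseline"). In Table 1, a positive antibody with HCV RNA not detected carries the label *Negative*.
- **Source of the baseline status.** "The baseline evaluation will be based on tests performed during the pre-treatment period". No second antibody assay is specified there.
- **A second assay after baseline only.** Footnote b to Table 1: "For post-baseline evaluation, a second antibody test with a different type of assay is to be done at the same date or after" the first one. The text below the table then replaces *Negative* by a confirmed antibody-positive, RNA-negative status when no RNA was detected and "the 2 antibody tests surrounding the same visit (from 2 different types of assay) are positive".
- **Definition of a conversion.** "Post-baseline seroconversion is defined for patients with a negative baseline status who had either a" positive-RNA status or that confirmed status after baseline. Anything else is left to case-by-case evaluation.

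On eligibility, Protocol 7.2.1 (E 29) lists among the excluding laboratory findings: "Positive test for Hepatitis C antibody (if positive, then confirmed by Hepatitis C Virus [HCV] polymerase chain reaction [PCR"]). On timing, SAP 2.1.4.3 puts the antibody test at Week -3 and at Week 64 or permanent treatment discontinuation.

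**The concern.** The same laboratory result is classified by two different rules, and the conversion count is the difference between them. A positive antibody with no RNA is *Negative* before treatment. After treatment it can be a confirmed positive, because a further test is then added. Take a patient with resolved infection whose antibody was present at screening and is still present at Week 64. The status changes because the rule changed, not because the patient did.

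Protocol 11.4.3.2 promises the number and percentage of patients with an observed seroconversion. One patient is 1/159 = 0.6% of all randomized patients, or 1/53 = 1.9% of an arm on full denominators, so a single misclassified patient is visible. The Week 64 tests fall in the open-label period, when every patient receives alirocumab and no concurrent placebo group is there to put such a case in context.

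**Working it through.** The plan states no figure for this endpoint, so the check is of the rule itself, followed by its possible scale.

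**1. Unchanged profiles put through the rule.** Take each combination of antibody (negative, positive) and RNA (not detected, detected, not available), held constant from baseline to post-baseline. For antibody-positive patients, cross this with the post-baseline second assay (positive, negative, not available). That gives 3 + 9 = 12 combinations. A correct conversion rule should count none of them.

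| Antibody / RNA, same at both times | Second assay after baseline | Baseline status | Post-baseline status | Counted? |
|---|---|---|---|---|
| Negative / not detected or not available (2 rows) | – | Negative | Negative | No |
| Negative / detected | – | Positive RNA | Positive RNA | No |
| Positive / detected (3 rows) | any | Positive RNA | Positive RNA | No |
| Positive / not available (3 rows) | any | Positive antibody, no RNA result | the same | No |
| Positive / not detected | negative | Negative | Negative | No |
| Positive / not detected | not available | Negative | Negative | No |
| Positive / not detected | **positive** | Negative | Confirmed antibody, RNA negative | **Yes** |

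One of the 12 is counted. If that baseline profile did not qualify as negative, none would be.

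**2. Can the profile be enrolled?** E 29 makes a positive antibody subject to PCR confirmation. An antibody-positive, PCR-negative patient is not a confirmed positive and so, on the natural reading, is not excluded. Table 1 supports this: its first footnote provides for the reflexive RNA test in the pre-treatment period, so the profile is foreseen at baseline.

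**3. Upper bound on the count.** The documents give no prevalence p of the profile, so it is an assumption here. Expected number enrolled = 159 × p. Chance of at least one = 1 − (1 − p)^159.

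| Assumed p | Expected enrolled | Chance of at least one enrolled |
|---|---|---|
| 0.5% | 0.8 | 55% |
| 1% | 1.6 | 80% |
| 2% | 3.2 | 96% |
| 3% | 4.8 | 99% |

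**4. Retesting shrinks this for the early tables.** The first-step cut-off is Week 24 (SAP section 3), so only patients who stopped early can have a post-baseline test in the double-blind and first-step tables. Use the dropout hazard in SAP 1.3 (30% in 12 months, exponential): proportion stopped by week w = 1 − 0.7^(w/52).

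- Check at Week 64: 1 − 0.7^(64/52) = 35.5%, which reproduces the plan's 36%.
- Week 12: 7.9%, or 12.6 of 159. Expected profiles among them: 12.6 × 0.005 = 0.06 to 12.6 × 0.03 = 0.38.
- Week 24: 15.2%, or 24.1 of 159. Expected: 24.1 × 0.005 = 0.12 to 24.1 × 0.03 = 0.72.

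This assumes that dropout means stopping treatment, that every early stopper is retested, and that the profile is unrelated to dropout. At the end of the study, retesting covers between 64% of patients (159 × 0.64 = 102, if no early stopper is tested) and all 159. All these counts fall further by the share whose second assay is not positive, which the documents do not give.

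**The case against.** Four points can be made in defence of the plan.

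- **The second assay is a safeguard.** A reader might infer that every antibody-positive, RNA-negative patient who is retested becomes a false case. The documents do not support that: if the second assay is negative or missing, the patient stays *Negative*. A false-positive first assay can be filtered out in this way. This limits the error but does not remove it, since a patient with true past infection would be expected to be positive on both assays.
- **Enrolment is not tabulation.** A reader might take the 55% to 99% as the chance of a false conversion in the report. It is only the chance that such a patient is enrolled, at a prevalence the documents do not give. For the double-blind and first-step tables the expected numbers are far smaller. This objection stands in full.
- **Eligibility is not settled.** E 29 could be read as excluding any positive antibody. It never says that a PCR-negative patient is eligible. The objection stands as a caveat, although the PCR clause and the pre-treatment RNA test in Table 1 both point towards eligibility.
- **The table is descriptive, and the error runs towards over-reporting.** This is true: SAP 2.4.5 plans no inferential safety tests, and the status that triggers the count is named separately from positive RNA. But the SAP invokes conservatism only for a positive antibody with no RNA result. It gives no reason for treating unchanged serology as a conversion.

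The case-by-case clause does not rescue the rule. It covers situations outside the definition, and this patient meets the definition.

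**Conclusion.** The definition is wrong as written for one profile: antibody positive and RNA not detected before and after baseline, with a positive second assay after baseline. That profile is counted as a seroconversion without any change in the patient.

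The size is small and uncertain. At an assumed prevalence of 0.5% to 3%, 0.8 to 4.8 of 159 patients would have the baseline profile. That bounds the false cases from above, because each must also be retested and confirmed on the second assay. The conclusion rests on reading E 29 as excluding only PCR-confirmed positives.

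A reader might infer that the trial's safety or efficacy conclusions are at risk. The documents do not support that: no efficacy result, alpha level or sample size is touched, and the effect stays within one descriptive safety table. The correction is still worth making, because one such patient would make that table wrong.

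**What to change.** Amend SAP 2.4.5.3 as follows:

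1. Give a baseline result of antibody positive with RNA not detected its own label instead of *Negative*.
2. Require a negative baseline antibody test for the antibody-based seroconversion criterion.
3. Count patients with the new baseline label as conversions only if RNA becomes detectable after baseline, and show them on a separate line.

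This keeps sensitivity to a true new infection and removes the one false route. The cost is SAP wording and one derivation change. It uses the screening antibody test and the reflexive RNA test already planned for antibody-positive patients, and needs no second antibody assay at baseline.

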2.4.5.4 Analyses of vital sign variables

The summary statistics (including number, mean, median, Q1, Q3, SD, minimum and maximum) of all vital signs variables (central laboratory values and changes from baseline) will be calculated for each visit or study assessment (baseline, each post-baseline value of the treatment period, last on-treatment, worst on-treatment value and follow-up visit) by treatment group. In addition for some parameters of interest; mean changes from baseline with the corresponding SE could be plotted over time (at same time points) in each treatment group.

Vital signs without position filled in will only be used for the PCSA analysis described below.

The incidence of PCSAs at any time during the TEAE period will be summarized by treatment group.

Analysis of vital signs variables in the open-label treatment period

For OLTP, summary tables as described for the DBTP above will be used with the following exception:

- Analysis by visit (unless data warrants further investigation)

Analysis of vital signs variables in the alirocumab exposed period (first step analysis only)

For alirocumab exposed period, summary tables as described for the DBTP above will be used with the following exception:

- Analyses by visit (unless data warrants further investigation)

2.4.5.5 Analyses of electrocardiogram variables

The count and percentage of patients with at least 1 abnormal ECG will be summarized by treatment group during TEAE period according to the following baseline status categories:

- Normal/missing;
- Abnormal.

2.4.6 Analyses of other endpoints

All measurements, scheduled or unscheduled, fasting or not fasting, will be assigned to analysis windows defined in [Section 2.5.4, Table 2](#) in order to provide an assessment for Week 4 to Week 64 time points.

HbA1c parameters will be summarized by analysis visit using number of available data, mean, SD, median, minimum, and maximum for each treatment group during the DBTP and OLTP. For HbA1c in DBTP, summary will be also provided according to the diabetes status at baseline defined in [Section 2.1.1](#). The time profile of each parameter will be also plotted by treatment group with the means and the corresponding SEs for HbA1c in DBTP. The incidence of PCSA at any time during the double-blind TEAE period will be also summarized on safety population by treatment group using descriptive statistics. PCSA for HbA1c will be also provided according to the diabetes status at baseline. The incidence of PCSA at any time during the open-label TEAE period (on OLT population) and during alirocumab exposed TEAE period (on alirocumab exposed population, at first step analysis only) will be also summarized using descriptive statistics. PCSA for HbA1c will be also provided according to the diabetes status at baseline.

Binary endpoints defined in [Section 2.1.5](#) will be described using count and percentage. [REDACTED]

[REDACTED] For the analysis of the time to the first of the 2 consecutive LDL-C, patients without post-baseline LDL-C result or with only 1 post-baseline LDL-C result will not be included.

2.4.7 Analyses of anti-alirocumab antibodies variables

The summary of ADA variables will be presented separately for the DBTP (on ADA population) and [REDACTED]

The following summaries will be performed, taking into account all samples regardless of timing in relation to injections but within each study period separately:

- [REDACTED]
- [REDACTED]
- [REDACTED]
- Number (%) of patients with pre-existing ADA and number (%) of patients with treatment-emergent ADA positive response
 - Number (%) of patients with persistent/transient/indeterminate treatment-emergent ADA positive response (for alirocumab exposed period and [REDACTED] ;
- Time to onset of treatment-emergent ADA positive response using descriptive statistics beginning from the first IMP administration within the relevant period [REDACTED]

2.4.8 Analyses of pharmacokinetic and pharmacodynamic variables

Serum total alirocumab concentration (alirocumab concentration, C_{trough} and $C_{follow-up}$), free and total PCSK9 concentrations will be summarized on the PK population by treatment group and visit using descriptive statistics. $C_{trough,av}$ will be summarized on the PK population by treatment group using descriptive statistics. Descriptive statistics could be provided by specific sub-groups (eg, gender, BMI, age), as needed.

Time profiles for C_{trough} concentration, total and free PCSK9 will be also provided by treatment group using graphs (mean \pm SE or Median, as appropriate).

2.5 DATA HANDLING CONVENTIONS

2.5.1 General conventions

The following formulas will be used for computation of parameters.

Time from diagnosis

Time from diagnosis (years) = (Date of informed consent – Date of diagnosis*) / 365.25.

(*): In case the month of diagnosis would be missing, it will be put equal to JANUARY if the year of diagnosis equals the year of informed consent; it will be put equal to JUNE otherwise.

Medical history

“Peripheral Arterial Disease” history is defined as follows, using combinations of the corresponding pre-listed medical history items of the e-CRF page “Cardiovascular history and cardiovascular risk factors”:

- Intermittent claudication (linked to PAD) TOGETHER WITH ankle-brachial index ≤ 0.90
Or
- Intermittent claudication (linked to PAD) TOGETHER WITH peripheral revascularization procedure (angioplasty, stenting) for PAD or peripheral revascularization surgery (arterial bypass) for PAD
Or
- Critical limb ischemia TOGETHER WITH peripheral revascularization procedure (angioplasty, stenting) for PAD or thrombolysis for PAD or peripheral revascularization surgery (arterial bypass) for PAD.

Date of last dose of IMP (for double-blind and for open-label)

The date of the last injection in the DBTP is equal to the last date of administration reported on injection administration case report form page in DBTP, or missing if the last administration date is unknown.

The date of the last injection in the OLTP is equal to the last date of administration reported on injection administration case report form page in OLTP, or missing if the last administration date is unknown.

Renal function formulas

estimated Glomerular filtration rate (eGFR) value will be derived using the Modification of the Diet in Renal Disease (MDRD) equation:

$$175 \times (\text{creatinine in } \mu\text{mol/L} / 88.4)^{-1.154} \times (\text{age in years})^{-0.203} (\times 0.742 \text{ if female, } \times 1.212 \text{ if race is "black or african american"})$$

Lipids variables, laboratory safety variables

For data below the lower limit of quantification (LLOQ)/limit of linearity, half of the lower limit value (ie, LLOQ/2) will be used for quantitative analyses. For data above the upper limit of quantification (ULOQ)/limit of linearity, the upper limit value (ie, ULOQ) will be used for quantitative analyses.

Pharmacokinetic variables

Data below the LLOQ are set to zero.

2.5.2 Data handling conventions for secondary efficacy variables

See [Section 2.1.3](#).

2.5.3 Missing data

For categorical variables, patients with missing data are not included in calculations of percentages unless otherwise specified. When relevant, the number of patients with missing data is presented.

Handling of baseline definition if time of first double-blind administration or time of assessment at Week 0 visit is missing

If the time of the first double-blind administration or the time of assessment at Week 0 visit is missing then the baseline value is defined as the last available value obtained before or on the day of the first double-blind IMP administration.

Handling of computation of treatment duration and compliance if investigational medicinal product first or end of treatment date is missing

If the last or first injection date is missing, the exposure duration and compliance will be left as missing.

Handling of safety and efficacy analysis periods and survival analysis if investigational medicinal product end of treatment date is missing

If the last injection date of DBTP or OLTP is missing, then this date is imputed to the earliest between:

- the last day of the month and year, when applicable or else the 31st of December of the year,
- the date of the end of treatment visit of the period (DBTP: Week 12 visit for patients who completed the double-blind study treatment period as per protocol, early end of treatment visit for patients who prematurely discontinued the IMP; OLTP: Week 64 visit for patients who completed the open-label study treatment period as per protocol, early end of treatment visit for patients who prematurely discontinued the IMP)
- and the date of the last contact,

for the purpose of safety and efficacy analysis period start and/or end.

The last dose intake should be clearly identified in the case report form and will not be approximated by the last returned package date.

Handling of medication missing/partial dates

No imputation of medication start/end dates or times will be performed. If a medication date or time is missing or partially missing and it cannot be determined whether it was taken prior or concomitantly, it will be considered a prior, concomitant, and posttreatment medication.

Handling of adverse events with missing or partial date/time of onset

Missing or partial AE dates and times will be imputed so that if the partial AE date/time information does not indicate that the AE started prior to treatment or after the TEAE period, the AE will be classified as treatment-emergent. These data imputations are for categorization purpose only and will not be used in listings. No imputation is planned for date/time of AE resolution.

Handling of adverse events when date and time of first investigational medicinal product administration is missing

When the date and time of the first double-blind IMP administration is missing, all adverse events that occurred on or after the day of randomization should be considered as treatment-emergent adverse events. The exposure duration should be kept as missing.

When the time of the first double-blind IMP administration is missing, all AEs that occurred on the day of the first double-blind IMP administration will be considered as TEAEs.

Handling of missing assessment of relationship of adverse events to investigational medicinal product

If the assessment of the relationship to IMP is missing, then the relationship to IMP has to be assumed and the adverse event considered as such in the frequency tables of possibly related adverse events, but no imputation should be done at the data level.

Handling of potentially clinically significant abnormalities

If a patient has a missing baseline value he will be grouped in the category “normal/missing at baseline”.

For PCSAs with 2 conditions, one based on a change from baseline value and the other on a threshold value or a normal range, with the first condition being missing, the PCSA will be based only on the second condition.

For a PCSA defined on a threshold and/or a normal range, this PCSA will be derived using this threshold if the normal range is missing; eg, for eosinophils the PCSA is >0.5 GIGA/L or $>\text{ULN}$ if $\text{ULN} \geq 0.5$ GIGA/L. When ULN is missing, the value 0.5 should be used.

Measurements flagged as invalid by the laboratory will not be summarized or taken into account in the computation of PCSA values.

